It is well recognized, but unclear why patients' perception of AF varies so much. This preliminary pilot trial will be used to estimate sample size for a larger trial, in which both patients and control subjects will be recruited, to further investigate whether patients with symptomatic AF have increased pain sensitization compared with patients with asymptomatic AF and controls. The studies may have an impact on individualized management of patients with AF in the future.

Material and methods

Study design

Single-center cohort study.

Subject inclusion criteria

Study participants will be recruited from a database of all patients aged 20 years or older with a diagnosis of AF from 1 January 2015 to 31 December 2018 in Örebro County (more than 10 000 patients) extracted from the National Patient Register, that covers all in-patient and outpatient physician visits from both private and public caregivers, and the Medrave 4 patient statistics software that is used in all public general practices in the county. The diagnosis of AF was based on at least one electrocardiogram (ECG) characterized by an absolutely irregular RR interval, no distinct P waves and an atrial cycle length of less than 200 ms. By accepted convention, an episode with these ECG characteristics lasting for at least 30 seconds was diagnostic of AF(8). Permanent AF is defined as persistent AF that is accepted by both the patient and the physician and for which no further attempts to restore or maintain normal sinus rhythm will be undertaken(8).

Further inclusion criteria:

- Male or female subjects \geq 20 years and \leq 75 year, primarily 60 to 70 years old.
- Permanent AF
- Previously completed AF-specific symptoms questionnaire Atrial fibrillation 6 questionnaire (AF6)
- Written informed consent

Subject exclusion criteria

Date: 2020-11-24

Version: 1.2

- Paroxysmal or persistent AF (AF that terminates spontaneously or with intervention, respectively(8))
- Previous pulmonary vein isolation
- Psychiatric or cognitive condition
- Pregnancy
- Previous/current drug or alcohol abuse
- Previous neurological or concomitant musculoskeletal disorders
- Continuous analgesic medication

Examinations

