A cardiovascular examination including blood pressure measurement will be performed. The blood pressure will be measured after 15 minutes of rest by an automatic sphygmomanometer.

Quantitative sensory testing

Pressure pain threshold

The pressure pain thresholds (PPTs) is defined as the minimal amount of pressure where a sense of pressure first changes to pain. Participants will be instructed to press the 'stop' button of the algometer as soon as the pressure results in the first sensation of pain.

Pressure will be increased at a rate of approximately 30 kPa/s. The 1-cm² probe of the handheld pressure algometer (Somedic AB, Sweden) will be placed perpendicularly to the skin. PPTs will be assessed over the sternum at the level of intercostal spaces 3–5 and over the tibia bone(27). The PPTs will be measured three times on each site, and the mean of the three measurements will be used for statistical analysis. Low PPTs indicate sensitization.

Temporal summation of pressure pain

A Pin prick (tip area, 0.2mm²) with a weighted load (Aalborg University, Denmark) will be used to induce temporal summation of pressure pain (TSP) as previously conducted in other pain studies(33-35). A force of 50 g will be applied once over the sternum at the level of intercostal spaces 3–5 and over the tibia bone and the patient will be asked to rate the pain intensity on the VAS (0 to 10). Then 10 consecutive stimuli will be applied (1 s interval between consecutive stimuli) to the same site and the subject will be asked to rate the pain intensity of the last stimulation on the VAS. TSP will be calculated as the difference in the

pain intensity between the first and the last stimulation. High TSP scores indicate facilitated temporal summation.

Conditioning pain modulation

The right hand up to the wrist will be immersed into stirred cold water (2–4 °C, measured in the water) for 2 min (the so called cold pressor test). Before the immersion the PPTs will be assessed from the sternum and the tibial bone, at the end of the two min immersion the PPTs will be assessed again and this will be repeated again 10 min after the hand is withdrawn from the water. The conditioning pain modulation index will be assessed as the increase in PPTs during the immersion as compared to the pre-immersion PPTs. The lower the difference is the more sensitization.

Primary endpoint

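### Surgery or scar at a test site, such as a previous sternotomy, is not an exclusion, so a local effect could shift the sternal pressure pain threshold

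*Combined protocol and SAP*

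**What the plan says.** All references are to the combined protocol and SAP.

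- **Test sites.** Under Quantitative sensory testing, "PPTs will be assessed over the sternum at the level of intercostal spaces" 3–5 and over the tibia. For temporal summation (TSP), "A force of 50 g will be applied once over the sternum at the level of intercostal spaces 3–5 and over the tibia bone". For conditioned pain modulation (CPM), "Before the immersion the PPTs will be assessed from the sternum and the tibial bone". There are two sites for all three tests. No alternative site is given, and no rule says when a reading is skipped or set aside.
- **Scoring.** "Low PPTs indicate sensitization", with no exception for a local cause. TSP is the rating of the last stimulus minus that of the first at the same site; "High TSP scores indicate facilitated temporal summation". CPM is the rise in PPT from its pre-immersion value at the same site.
- **Exclusions.** There are seven. The nearest is "Previous neurological or concomitant musculoskeletal disorders". Two others, on earlier pulmonary vein isolation and on continuous analgesics, touch the question only at its edges. None names sternotomy, heart surgery, a scar, or altered sensation at a test site.
- **Analysis.** Groups are formed from previous AF6 scores. Age is the only adjustment planned under Statistical analysis. Comorbidities, a chest-pain rating and a pain drawing are collected at the visit, but nothing links them to the handling of sternal readings.

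**The concern.** The Hypothesis section concerns central sensitization and predicts lower pain thresholds in symptomatic patients. A reading taken near a healed sternotomy may differ because of the local tissue. Tenderness would lower the sternal PPT and imitate the hypothesised effect; numbness would raise it and hide the effect. A patient with permanent AF, within the age range, with previous open-heart surgery and no daily analgesic could meet every criterion as written.

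The groups are not randomised, so equal surgical history cannot be presumed. At stake are the sternal PPT comparison and the sternal PPT spread that the pilot would hand to the larger study.

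**Working it through.** The plan derives no sample size, power or effect size, so there is no figure of its own to reproduce. The size has to be illustrated.

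**Inputs from the document:** 15 patients per group; two sites; scoring as above.

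**Assumed inputs (not in the document):** k = 1–3 sternotomy patients in one group and none in the other; sternal PPT shifted by s = 30–50% in each, all in the same direction; between-patient coefficient of variation CV = 0.3–0.5.

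**1. False difference in sternal PPT.** Shift of the group mean = (k/15) × s; in SD units, divide by CV.

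- Smallest: (1/15) × 30% = 2.0%; 0.020/0.5 = 0.04 SD.
- Two patients, 50% shift: (2/15) × 50% = 6.7%; 0.067/0.5 = 0.13 SD to 0.067/0.3 = 0.22 SD.
- Largest: (3/15) × 50% = 10%; 0.10/0.3 = 0.33 SD.

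**2. Comparison with chance variation.** The standard error of the difference between two groups of 15 is √(2/15) = 0.365 SD. The largest case is 0.33/0.365 = 0.91 standard errors.

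**3. Mixed directions.** If one of two affected patients in a group has a PPT 50% lower and the other 50% higher, the mean shift is (1/15)(−50% + 50%) = 0. Only the spread grows.

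**4. Equal rates in both groups.** With an assumed rate p and local shift d in SD units, the SD is multiplied by √(1 + p(1 − p)d²).

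- p = 5%, d = 0.5: √1.012 = 1.006, a rise of 0.6%.
- p = 20%, d = 1.5: √1.36 = 1.166, a rise of 17%.

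Required sample size goes with the square of the SD, so it would rise by about 1% to 36% over this range.

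**5. Chance that the issue arises.** The probability of at least one such patient among 30 is 1 − (1 − p)³⁰: 79% at an assumed 5% and 96% at 10%. The probability that the groups differ by two or more patients, with the same underlying rate in both, is 19% and 35%.

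**6. TSP and CPM.** Both subtract two readings at one site. If the local effect adds a constant c, then (a + c) − (b + c) = a − b and it drops out. A local effect that is not constant would leave some trace, so cancellation is partial. The document gives nothing from which to size the remainder.

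**The case against.** The strongest reply is that nothing in the document shows that such patients will occur, or occur unequally. Heart surgery is not mentioned, and every input to the size is assumed. The arithmetic in step 1 also takes the unfavourable case: all affected patients in one group and all shifts the same way. Even then the result stays under one standard error, in a pilot that is not a confirmatory test. This stands, and it limits the size of the point.

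Safeguards also exist. The tibia is tested in every procedure, so a purely local sternal effect should show as a discrepancy between sites. Some patients with nerve injury or persistent chest-wall pain would be removed by the neurological, musculoskeletal or analgesic criteria. Comorbidities are recorded, and their association with sensitization is a secondary objective. These help, but the plan does not say which site is primary or how the two are combined, and surgical history is not named among the items recorded.

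A reader might infer three stronger things that the document does not support:

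- **That all three sternal measures are distorted alike.** TSP and CPM are within-site differences, in which a constant shift cancels.
- **That the probe would rest on the scar line.** The text gives a region of the sternum, not the midline.
- **That the SD passed to the larger study is inflated.** This is so only if that study excludes these patients. If its eligibility is the same, an SD that includes them is the right planning value.

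**Conclusion.** The gap is real. As written, the criteria allow a patient with a healed sternotomy to be enrolled, and a locally altered sternal PPT would be read as more or less sensitization. The point is mainly about absolute PPT at the sternum. It applies less to sternal TSP and CPM, and a sternotomy does not touch the tibial readings.

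Under the assumed inputs the false difference is 0.04–0.33 SD, below one standard error of 0.365 SD. Bias between groups needs unequal frequency or unequal effect; otherwise the result is mainly added variance. The document supplies no sternotomy rate, local shift or PPT standard deviation, so neither the direction nor the actual size can be established, and it would be wrong to conclude that the pilot's group comparison is biased. This is a modest improvement, worth making because it is cheap.

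**What to change.** Choose one of two options before enrolment.

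1. **Exclude.** Add a line to Subject exclusion criteria: *previous sternotomy or other surgery, scar or injury at a test site (sternum or anterior tibia)*. It can be checked at the telephone contact or in the hospital record. The cost is a slightly smaller eligible pool and slightly narrower generalisability. Only 30 patients are sought, and the source database covers AF patients "in Örebro County (more than 10 000 patients) extracted from the National Patient Register" and the general-practice system.
2. **Record and omit.** Add the item to the case report form and pre-specify that readings at the affected site are left out while the other site is kept. The cost is a few missing sternal readings. If three of 15 were lost in one group, the standard error would go from 0.365 to √(1/12 + 1/15) = 0.387 SD, about 6% more.

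Whichever is chosen, the larger study should use the same rule, so that the pilot's sternal SD applies to the population it is used to plan for.

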Pain sensitization in patients with symptomatic atrial fibrillation compared with asymptomatic patients

[name], PhD¹, [name], BSc¹ [name], PhD¹, [name] BSc PhD², [name], MSci, PhD, DMSci²

1. Department of Cardiology, Faculty of Medicine and Health, Örebro University, Sweden.
2. SMI, Faculty of Medicine, Aalborg University, Aalborg, Denmark.

Correspondence:

[name], PhD

[name], PhD

Department of Cardiology

Department of Cardiology

Örebro University Hospital

Örebro University Hospital

[name]

[name]

[contact]

[contact]

[contact]

[contact]

Email: [contact]

Email: [contact]

Abstract

Background

Atrial fibrillation (AF) is the most common sustained arrhythmia and the number of patients with AF is expected to increase substantially in the coming decades. One third of patients with AF report no AF-associated symptoms, but up to one fourth report severe symptoms such as chest pain. It is well recognized, but unclear why patients' experience of AF-related symptoms, including chest pain, varies so much. Patients with chronic pain show a high degree of central sensitization, i.e. facilitated pain responses to repeated painful stimulation and impaired conditioned pain modulation, compared with controls. It is possible that patients with symptomatic AF may have developed pronounced pain sensitization even in the absence of chest pain as a symptom. No previous study has investigated pain sensitization in patients with AF.

Objective and methods

The primary objective is to assess differences in pain sensitization in patients with symptomatic AF compared with patients with asymptomatic AF. Secondary objectives are to study the association of age, sex, AF duration, comorbidities and health-related quality of life to pain sensitization. A total of 30 patients with permanent AF (15 symptomatic and 15 asymptomatic) will be recruited. Patients will complete an AF-specific symptom score and a generic health-related quality of life questionnaire, and physicians will assess AF-related symptoms. Quantitative sensory testing recordings will be collected by pressure algometry. Assessment of temporal summation of pressure pain and conditioning pain modulation will be used to investigate the involvement of pain sensitization.

Clinical relevance

Date: 2020-11-24

Version: 1.2

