The primary objective is to assess differences in pain sensitization in patients with symptomatic AF compared with patients with asymptomatic AF.

Secondary endpoint

Secondary objectives are to study the association of age, sex, AF duration and comorbidities and physical and mental component summary scores to pain sensitization.

Ethics approval

The study protocol is approved by the Swedish Ethical Review Authority (2020-01619).

Statistics and data management

Date: 2020-11-24

Version: 1.2

Data collected during the study will be coded.

Statistical analysis

Data will be presented as mean and standard deviation. A one-way ANOVA will be used for demographic parameters and to compare the groups. Pearson correlations will be used for linear estimates and Spearman's correlations for non-linear parameters. All analyses will be adjusted for age. Analyses will be performed using IBM SPSS Statistics 22 (Armonk, NY, USA) or STATA release 14 (College Station, TX, USA).

Sample size calculations

As no previous trial of pain sensitization in patients with AF has been performed, a pilot trial is necessary to calculate sample size for a larger study.

Database and Case report form

A case report form will be filled out and coded for each patient. The investigators are responsible for ensuring the accuracy, completeness, legibility and timeliness of the data recorded in the case report forms.

Documentation and data collection

Criteria for inclusion, informed consent, the decision to include the subject and the subject number will be documented in the subject's hospital record.

Insurance

The subjects in the study are covered by the Swedish patient insurances.

Economy

The trial is an academic study conceived and conducted by healthcare personnel. The study is independent of commercial interests. Study logistics, handling of data and statistical

assessment will be financed by the Department of Cardiology, Örebro University Hospital, Sweden. The investigators will apply for grants from public funds.

Ethical considerations

The study will be conducted in accordance with the Declaration of Helsinki. The cold pressor test activates the sympathetic nervous system and increases blood pressure and heart rate, and there is a slight risk of angina during the test. There are otherwise no known risks or complications associated with the quantitative sensory testing but it may cause some temporary mild to moderate discomfort.

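### Does adjusting every analysis for age make the secondary question about age unanswerable?

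*Combined protocol and SAP*

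**What the plan says.** The Secondary endpoint section reads: "Secondary objectives are to study the association of age, sex, AF duration and comorbidities and physical and mental component summary scores to pain sensitization". The Abstract (Objective and methods) gives the same aim in slightly different words: "Secondary objectives are to study the association of age, sex, AF duration, comorbidities and health-related quality of life to pain sensitization". Age comes first in both lists.

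The Statistical analysis section is one short paragraph. For groups it says "A one-way ANOVA will be used for demographic parameters and to compare the groups". For associations it says "Pearson correlations will be used for linear estimates", with Spearman's coefficient where the relation is not linear. It then adds "All analyses will be adjusted for age". Descriptively, "Data will be presented as mean and standard deviation". The section does not list the demographic parameters, names no regression model, does not say how the adjustment is carried out, and exempts nothing from it.

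**The concern.** Two statements a few lines apart seem to exclude each other. One makes age a factor to be studied; the other removes the effect of age from every analysis. If both are obeyed to the letter, one named secondary association has no estimate. If age is also one of the demographic parameters tested between groups, its age-adjusted difference is zero by construction and has no test.

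A second difficulty sits in the same sentence. One-way ANOVA and ordinary Pearson or Spearman coefficients take no covariate, so the plan promises an adjustment that its named methods do not provide in their plain form.

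Age is not a trivial variable here. The Introduction reports that asymptomatic AF is more frequent at older ages, so the two groups may differ in age. If the plan really left the age question without an answer, the pilot would lose information that could help in choosing covariates for the larger study.

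**Working it through.** **Inputs.** The adjustment rule and the methods come from Statistical analysis, and the list of factors from Secondary endpoint. The sample is 30 patients, 15 per group (Abstract). The plan gives no effect size, SD, alpha or power, so it has no figure of its own to reproduce. The check is algebraic.

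**1. Age as the factor, adjusted for age.** Write A for age and Y for a pain measure. The partial correlation is

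r(A,Y|A) = (r_AY − r_AA × r_AY) / √[(1 − r_AA²)(1 − r_AY²)].

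With r_AA = 1 this is (r_AY − r_AY) / √[0 × (1 − r_AY²)] = 0/0 whatever r_AY is. Equivalently, a design with columns [1, age, age] has rank 2 of 3. A simulated sample of 30, with ages assumed uniform between 60 and 70, gave the same result: residual variance of age 0, numerator 0, denominator 0.

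**2. Age as the variable compared.** Regress age on group and age. The group coefficient is 0 and the residual sum of squares is 0, so F = 0/0. This arises only if age is among the tested demographic parameters. The group means and SDs of age are shown either way.

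**3. Any other factor, adjusted for age.** For a factor X that is not perfectly correlated with age, 1 − r_XA² is above 0 and the partial correlation can be computed. In the same simulated sample, the age-adjusted correlation for an invented AF duration came out at −0.32. That value says nothing about the trial; it shows only that the calculation runs.

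**4. Age as a term in a model.** A design with columns [1, group, age] has rank 3 of 3. The model that adjusts the group comparison for age therefore also yields an estimable age coefficient. The ordinary correlation of age with a pain measure is estimable too.

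**5. The unnamed methods.** A one-way ANOVA with age as covariate is ANCOVA. A Pearson or Spearman correlation adjusted for age is the corresponding partial correlation. These are the routine counterparts of the methods the plan names.

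The literal contradiction is real, then, but it is confined to age adjusted for itself. There the calculation stops visibly instead of giving a plausible wrong answer.

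**The case for a change.** The best case for a change is that the exemption is not unique. An analyst might report the crude correlation of age with a pain measure across all 30 patients, or the age coefficient from a model that also contains group. These answer different questions, because the groups are chosen from the extremes of the AF6 score (0 versus at least 30).

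An illustration with assumed values: let age and a pain measure each differ by 0.8 within-group SD between two equal groups, and be uncorrelated within groups. The between-group part of the covariance is 0.4 × 0.4 = 0.16. Each total variance is 1 + 0.16 = 1.16. The pooled correlation is 0.16/1.16 = 0.14 in absolute value, whereas the within-group association is 0.

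That distinction is correct, but it does not turn on the missing exception. Exempting age from age adjustment does not by itself settle whether group should be in the model, and the same choice exists for every other listed factor. The plan also names correlations for associations, so the natural default is the simple coefficient. For scale, a correlation of 0 in 30 patients has a 95% interval of −0.36 to 0.36 (Fisher z, standard error 1/√27), much wider than the 0.14 in the illustration.

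It is also fair to say that the clarification would cost only one sentence. Low cost does not make it necessary when nothing in the results depends on it.

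**Conclusion.** No change is called for. The plan omits an obvious exception, and analysts fill that gap sensibly. Read together, the two sections mean that age is studied as a factor and the remaining analyses are adjusted for it. The slip reaches one listed secondary factor, plus at most one baseline test that serves no stated objective. It introduces no bias, costs no power and leaves the primary comparison and the other associations as they were.

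No count of lost associations is given here. It would depend on how many pain measures, sites and comorbidities are analysed, which the plan leaves open, and it would not measure any harm.

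The conclusion assumes that whoever runs the analysis will not partial age out of itself, an attempt that would fail openly. It also rests on the stated purpose of the study, in Clinical relevance and Sample size calculations, as a pilot for planning a larger one. The sponsor may add a clarifying clause at the next routine revision, but the analysis does not depend on it.
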